3.2.3 Mapping of assessments performed at Premature End of Treatment Visit

Efficacy and safety assessments at a Premature End of Treatment Visit (PEOT) that correspond to a scheduled visit will be summarized at the next scheduled visit.

In particular, clinical laboratory parameters, vital signs, ECG and exploratory safety biomarkers are assessed at all Treatment Period visits, and so all assessments of these variables at PEOT corresponding to a scheduled visit will be mapped to the corresponding scheduled visit.

3.3 Definition of Baseline values

Baseline will be the last available predose value prior to the first infusion of study drug in Dosing Period 1, or if missing, the Screening values. Scheduled or unscheduled measurements can be used as the Baseline value. Expected measurement-specific Baseline time points are presented in Table 3–1. If an unscheduled measurement occurs after the planned baseline measurement time point but before dosing, then the unscheduled measurement will be used.

Table 3–1: Expected Baseline Visits

Measurement	Baseline
Safety data 
 • Clinical Chemistry • Hematology • Urinalysis • ECG • Vital signs • [REDACTED] • [REDACTED] • [REDACTED] • Body weight 	
 • Clinical chemistry, Hematology, Urinalysis, ECG and Vital signs: Predose Day 1 or if missing the Screening value • [REDACTED] [REDACTED] [REDACTED]: Predose Day 1 • Body weight: screening visit

Table 3–1: Expected Baseline Visits

Measurement	Baseline
Pharmacodynamic data 
 Total serum IgG Serum IgG subclass concentrations MG specific antibodies (██████████) 	
 Total serum IgG and Serum IgG subclass: Predose Day 1 or if missing the Screening value Mg-specific autoantibodies: Predose Day 1
Immunological data: 
 IgM, IgE, IgA Serum complement levels (C3 and C4) and plasma complement levels (C3a and C5a) ██████████ Serum BAFF levels Cytokines ██████████ specific IgG antibodies Exploratory biomarkers relating to mechanism of action, disease activity, treatment response, and clinical outcome 	
 IgM, IgE, IgA, C3, C4, C3a, C5a, ██████████, BAFF, cytokines: Predose Day 1 ██████████ antibodies: Screening Exploratory biomarkers: Predose Day 1
Efficacy data: 
 QMG scale MG-composite scale MGADL MGFA scale MG muscle weakness Fatigue MGII SFEMG 	
 QMG, MG composite scale and MGFA: Predose Day 1 or if missing the Screening value MGADL, Muscle weakness, Fatigue scale, MGII, SFEMG: Predose Day 1.

██████████ BAFF=B-cell activating factor ; Ig=immunoglobulin; MGADL=myasthenia gravis-Activities of Daily Living; MGFA=Myasthenia Gravis Foundation of America; MGII= Myasthenia Gravis Impairment Index; SFEMG=single fiber electromyography; QMG=quantitative myasthenia gravis

3.4 Protocol deviations

Important protocol deviations are deviations from the protocol which potentially could have a meaningful impact on study conduct or on the primary efficacy, key safety, or PK/PD outcomes (if applicable) for an individual subject. The criteria for identifying important protocol deviations will be defined within the appropriate protocol-specific document. Important protocol deviations will be reviewed as part of the ongoing data cleaning process and data evaluation. All important deviations will be identified and documented prior to unblinding to confirm exclusion from analysis sets.

3.5 Analysis sets

3.5.1 Enrolled Set

The Enrolled Set (ES) will consist of all subjects who have given informed consent.

3.5.2 Randomized Set

The Randomized Set (RS) will consist of all subjects randomized into the study at the first randomization visit.

3.5.3 Safety Set

The Safety Set (SS) will consist of all subjects in the RS, who have received at least 1 dose of IMP.

Safety and immunological variables will be analyzed using the SS.

It is expected that subjects will receive treatment as randomized and hence safety analyses will be based on the randomized treatment group. However, if after unblinding it is determined that a subject has received the incorrect treatment based on the randomization schedule, then for safety analyses the subject will be allocated to the actual treatment they received in the respective Dosing Period.

3.5.4 Full Analysis Set

The FAS will consist of all subjects in the SS, who have a Baseline and least 1 post-Baseline QMG measurement during Dosing Period 1 (up to and including Visit 9, ie, Day 29).

The FAS is the primary analysis set for efficacy analyses. As for the SS, in the case of mistreatment, subjects will be primarily analyzed as treated. However, if applicable, sensitivity analysis will also be performed according to the randomized treatment group.

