3.5.5 Per Protocol Set

The Per-Protocol Set (PPS) is a subset of the FAS, consisting of those subjects who had no important protocol deviations affecting the primary efficacy variable, as confirmed during a pre-analysis data review meeting conducted prior to study unblinding. Post-Baseline deviations will not necessarily lead to total exclusion of a subject from the PPS but may lead to exclusion of specific data. In the case of mistreatment the subject will be analyzed as randomized.

Analysis of the primary efficacy variable will be repeated using the PPS.

3.5.6 Pharmacokinetic Per-Protocol Set:

The PK-PPS is a subset of the FAS, consisting of those subjects who had no important protocol deviations affecting the plasma concentration of UCB7665.

3.5.7 Pharmacodynamic Per-Protocol Set:

The PD-PPS is a subset of the FAS, consisting of those subjects who had no important protocol deviation affecting the serum concentrations of total serum IgG or IgG subclasses. As for the SS in the case of mistreatment, subjects will be primarily analyzed as treated.

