3.6 Treatment assignment and treatment groups

Safety, PK, PD and efficacy analyses will be assigned treatment as described in [Section 3.5](#).

Analyses will be performed by treatment group and for all subjects (if applicable) as described in [Section 3.1](#).

The Treatment Groups for Dosing Period 1 will be as follows:

- Placebo
- UCB7665 7mg/kg

For Dosing Period 2 and the Observation Period the following treatment groups will be considered for analysis and will be displayed as such in the TFLs (the first two groups will only be utilized for observation period in case patients do not receive any dosing in period 2):

- Placebo
- UCB7665 7mg/kg
- Placebo - UCB7665 7mg/kg
- Placebo - UCB7665 4mg/kg
- UCB7665 7mg/kg - UCB7665 7mg/kg
- UCB7665 7mg/kg - UCB7665 4mg/kg

These Treatment Groups will be used for all analyses.

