8.1.2 Primary analysis of the primary efficacy variable

A 1-sided hypothesis test will be performed to test the primary hypothesis of superiority of UCB7665 7mg/kg vs placebo at Visit 9. The null hypothesis is that the mean change from Baseline in QMG score is larger or equal in the UCB7665 7mg/kg group than the placebo group. The alternative hypothesis is that the mean change from Baseline in QMG score is smaller in the UCB7665 7mg/kg group than the placebo group.

The primary analysis of the primary variable will be analyzed for the FAS using a mixed model repeated measures (MMRM) analysis of covariance (ANCOVA) that includes terms for week (as categorical effect), treatment group, the Baseline QMG score, and the interaction between treatment group and week. The model will define subject as a random effect and utilize an unstructured covariance pattern. Least Squares (LS) Means for changes from Baseline at Visit 9 (Day 29) for each treatment group will be presented together with LS mean differences (UCB7665 - 7mg/kg vs placebo), p-value and 1 sided 95% CI.

For subjects who prematurely withdraw for any reason before Visit 9 (Day 29), data collected during the PEOT Visit will be used to impute QMG scores at the next consecutive visit.

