8.1.3 Supportive and sensitivity analyses of the primary efficacy variable

Different sensitivity analyses to evaluate the effect of missing observations on the primary analysis findings will be done. The first sensitivity analysis will be performed in the same way as the primary analysis but will use PPS instead. A further analysis will utilize the Last Observation Carried Forward (LOCF) approach and the FAS; missing values will be replaced by the last observed post-Baseline value of the variable and the analysis will be performed on the resulting dataset.

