8.2.1 MG-composite score

The MG-composite score will be analyzed utilizing the MMRM ANCOVA. A 1-sided hypothesis test will be performed to test the hypothesis of superiority of UCB7665 7mg/kg vs placebo at Visit 9. The null hypothesis is that the mean change from Baseline in MG-composite score is larger or equal in the UCB7665 7mg/kg group than the placebo group. The alternative hypothesis is that the mean change from Baseline in MG-composite score is smaller in the UCB7665 7mg/kg group than the placebo group.

The change from baseline of the MG-composite score will be analyzed for the FAS using a MMRM ANCOVA that includes terms for week (as categorical effect), treatment group, the Baseline MG-composite score, and the interaction between treatment group and week. The model will define subject as a random effect and utilize an unstructured covariance pattern. Least Squares (LS) Means for changes from Baseline at Visit 9 (Day 29) for each treatment group will be presented together with LS mean differences (UCB7665 - 7mg/kg vs placebo), p-value and 1 sided 95% CI.

For subjects who prematurely withdraw for any reason before Visit 9 (Day 29), data collected during the PEOT Visit will be used to impute MG-composite scores at the next consecutive

visit.. There will be no sensitivity analysis for the MG-composite score. Subjects without baseline value will not be analyzed.

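### The FAS, which carries the primary superiority test, groups mistreated subjects as treated and leaves as-randomised grouping to a conditional sensitivity analysis; the two should change places.

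*SAP*

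**What the plan says.** - **FAS (SAP 3.5.4; the same rule in the protocol's FAS definition in section 14).** Under "mistreatment, subjects will be primarily analyzed as treated", the actual product determines the arm. The alternative is then offered: "if applicable, sensitivity analysis will also be performed according to the randomized treatment group".
- **Primary test (SAP 8.1.2).** "The primary analysis of the primary variable will be analyzed for the FAS using a mixed model repeated measures" model, tested 1-sided at 0.05 (SAP 3.1). SAP 3.6 carries the set-specific grouping into efficacy: "Safety, PK, PD and efficacy analyses will be assigned treatment as described in" section 3.5.
- **PPS (SAP 3.5.5).** The grouping is the opposite: "In the case of mistreatment the subject will be analyzed as randomized". The protocol's PPS definition has no sentence on mistreatment.
- **Sensitivity analyses.** SAP 8.1.3 lists the PPS and LOCF analyses: "The first sensitivity analysis will be performed in the same way as the primary analysis but will use PPS instead". The as-randomised FAS analysis is not listed there. For a secondary endpoint, SAP 8.2.1 states: "There will be no sensitivity analysis for the MG-composite score". SAP 8.2.2 says the same for MGADL.
- **What counts as actual treatment.** The FAS rule points to the Safety Set (SAP 3.5.3), which assigns a subject to the product received in the Dosing Period. Dosing Period 1 has three infusions.

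**The concern.** Randomisation balances the arms on prognosis, measured and unmeasured. Analysis by randomised arm keeps that balance whatever caused a dispensing error. Moving a subject to the arm of the product received keeps it only if the error was unrelated to prognosis, apart from what the Baseline QMG covariate absorbs. With about 20 subjects per arm, one relabelled subject carries roughly 5% of an arm's mean. The plan gives the headline 1-sided test to the grouping that needs the extra assumption, and gives the grouping that does not need it a conditional supporting role. Analysing as treated is normal for safety; the point concerns the efficacy test only.

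**Working it through.** **Nothing to reproduce.** The documents give no figure on mistreatment. The effect, SD and significance level in the sample-size text are redacted, so the sample size cannot be reproduced, and nothing here suggests that it is wrong.

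**Inputs.** From the documents: 40 evaluable subjects allocated 1:1 (20 per arm), 1-sided 0.05, Baseline QMG as covariate. Assumed: one mistreated subject, SD 3.5 (range 3.0 to 4.0), effect 3.0 to 3.4 points (3.4 appears only in the amendment log, which describes superseded text), and a correlation of 0.3 to 0.5 between an unmeasured prognostic factor and the Baseline-adjusted outcome.

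**Mechanism by hand.** There is no drug effect. One placebo-randomised subject receives active and is expected to do b SD better than average. As treated, the arms have 19 and 21 subjects, and the expected difference is

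b × (1/19 + 1/21) = 0.100 b SD, with standard error √(1/19 + 1/21) = 0.317 SD.

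For b = 0.5, the shift is 0.050 SD (0.050 × 3.5 = 0.18 points), or 0.050/0.317 = 0.158 standard errors. Type I error is then about P(Z > 1.645 − 0.158) = 0.069. If the subject is expected to do 0.5 SD worse, it is P(Z > 1.645 + 0.158) = 0.036. By randomised arm, the expected difference is zero.

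**Simulation.** 20 per arm, one placebo-randomised subject given active, ANCOVA with Baseline (a single-visit simplification of the planned MMRM), no drug effect. There were 400,000 trials per scenario, or 200,000 for the Baseline-linked rows.

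| How the mistreated subject arises | Type I error, as treated |
|---|---|
| At random | 0.050 |
| Linked to Baseline QMG only | 0.050 to 0.051 |
| Unmeasured prognosis, better half (correlation 0.3 / 0.5) | 0.058 / 0.062 |
| Best quarter | 0.063 / 0.071 |
| Worse half | 0.042 / 0.038 |
| Worst quarter | 0.039 / 0.032 |

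By randomised arm, every scenario gives 0.049 to 0.051. The as-treated bias in the unmeasured-prognosis rows is 0.07 to 0.20 QMG points at SD 3.5.

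**Price of as-randomised grouping.** One fully mistreated placebo subject dilutes the estimate by effect/20: 3.4/20 = 0.17 points, or 3.0/20 = 0.15. Power by ANCOVA at SD 3.5, with Baseline assumed uncorrelated with change:

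| Effect | As treated | As randomised | Loss |
|---|---|---|---|
| 3.4 | 0.907 | 0.876 | 3.1 points |
| 3.0 | 0.835 | 0.799 | 3.6 points |

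Across SD 3.0 to 4.0 the loss is about 2 to 4 points. If Baseline correlates 0.4 with change, the first row becomes 0.944 and 0.920, a loss of 2.4 points.

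**The case against.** The strongest reply is that the choice is openly pre-specified and both groupings are promised, so any discrepancy would be visible. This is a Phase 2a study meant to inform later trials. Kits are allocated by the IRT and staff give the infusions, so mistreatment should be rare. Investigators and subjects are blinded, so a kit error is most plausibly unrelated to prognosis, and in that case as-treated grouping holds its level. All of this stands, and it keeps the point small. It does not explain why the grouping that needs an extra assumption should be primary.

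Four stronger readings are tempting, and the documents do not support them:

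- **That the primary test is expected to have inflated error.** There is no mistreatment rate and no stated mechanism linking errors to prognosis. Under such a link the error can equally fall below 0.05.
- **That the error could reach 0.09.** Selecting the mistreated subject on the Day 29 outcome itself gives 0.073 to 0.091 for good outcomes and 0.027 to 0.020 for poor ones. Dosing Period 1 infusions end at Visit 6 (Day 15), before that outcome exists, so these figures are only a theoretical bound.
- **That a subject given both products would be placed in an arm with treatment known.** The trigger "if after unblinding it is determined that a subject has received the incorrect treatment based on the randomization schedule" is written for safety analyses. SAP 7 sends dosing deviations to the data evaluation meeting, and SAP 3.4 requires important deviations to be documented before unblinding, under criteria in a document not available here. What remains is narrower: neither section gives a rule for assigning such a subject to an arm.
- **That the PPS rule is itself an error.** The PPS already drops subjects or data with important deviations, so its as-randomised sentence matters mainly for late discoveries. The conflict with the FAS disappears once the FAS is grouped by randomised arm.

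**Conclusion.** The point holds as a minor, inexpensive improvement to the choice of primary grouping. It is inactive unless a subject receives the wrong product in Dosing Period 1, and harmless to type I error if that happens at random or in relation to Baseline QMG only. If it is linked to other prognosis, one such subject moves the as-treated level to between about 0.03 and 0.07, while as-randomised grouping holds 0.05. That range rests on 20 per arm, the assumed correlations of 0.3 to 0.5 and a single-visit ANCOVA in place of the MMRM.

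Two details are simply missing. It is not stated whether the as-randomised analysis extends to the secondary endpoints, for which sensitivity analyses are ruled out. Nor is it stated how a subject with mixed infusions is grouped in the as-treated analysis.

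**What to change.** 1. In SAP 3.5.4, group the FAS by randomised arm for the primary and secondary efficacy tests, with as-treated grouping as the sensitivity analysis if mistreatment occurs. Make the same change to the protocol's FAS definition at its next amendment.
2. In SAP 8.1.3, 8.2.1 and 8.2.2, name the endpoints that receive the as-treated analysis.
3. As a secondary clarification, state before unblinding how a subject who received both products in Dosing Period 1 is grouped in the as-treated analysis. One option is to count any active infusion as UCB7665 7mg/kg.
4. Keep the PPS sentence, which then agrees with the FAS, and leave the Safety Set as treated.

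The cost is a SAP text amendment before unblinding and one protocol sentence, with no new data. The statistical price is the power loss shown above, paid only if someone is mistreated.

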3.5.5 Per Protocol Set

The Per-Protocol Set (PPS) is a subset of the FAS, consisting of those subjects who had no important protocol deviations affecting the primary efficacy variable, as confirmed during a pre-analysis data review meeting conducted prior to study unblinding. Post-Baseline deviations will not necessarily lead to total exclusion of a subject from the PPS but may lead to exclusion of specific data. In the case of mistreatment the subject will be analyzed as randomized.

Analysis of the primary efficacy variable will be repeated using the PPS.

3.5.6 Pharmacokinetic Per-Protocol Set:

The PK-PPS is a subset of the FAS, consisting of those subjects who had no important protocol deviations affecting the plasma concentration of UCB7665.

3.5.7 Pharmacodynamic Per-Protocol Set:

The PD-PPS is a subset of the FAS, consisting of those subjects who had no important protocol deviation affecting the serum concentrations of total serum IgG or IgG subclasses. As for the SS in the case of mistreatment, subjects will be primarily analyzed as treated.

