As individual disease entities, IgG autoantibody mediated conditions are relatively rare. Treatment of these disorders remains a difficult clinical problem, requiring in many of these conditions the long-term use of high-dose corticosteroids alone or combined with cytotoxic agents. These therapeutic approaches are not effective in all patients and conditions and have broad immunosuppressive effects causing considerable toxicity and treatment-related morbidity. Treatments aimed at reducing the quantity of circulating IgG autoantibody, including plasmapheresis, immunoadsorption, or high-dose intravenous immunoglobulin (IVIg), are being used for primary and secondary therapy of autoimmune disease, particularly where atiations thereof corticosteroid-based immune suppression is not or no longer effective (eg, immune thrombocytopenic purpura [ITP], MG, and chronic inflammatory demyelinating polyradiculoneuropathy). The therapeutic approach of these treatments is thought to be based on lowering levels of pathogenic autoantibodies, which represents rational and effective treatment modalities of autoimmune diseases.

Myasthenia gravis is a rare autoimmune disorder of the peripheral motor system in which autoimmune antibodies most commonly form

at the neuromuscular junction (NMJ). The autoantibody impairs the ability of to bind to receptors, and leads to the destruction of receptors, either by inducing the muscle cell to eliminate the receptors through endocytosis or by complement fixation. A second category of MG is due to autoantibodies against the

which is required for the formation of the NMJ. Antibodies inhibit signaling, resulting in a decrease in patency of the NMJ, and the against consequent symptoms of MG. In both categories, this results in a characteristic pattern of progressively reduced muscle strength with repeated muscle use and muscle strength recovery following a period of rest. Additional antibodies have been found to be associated with MG but less is yet known about them and they appear less common than the main two. The essential role of the autoimmune antibodies in mediating this pathology is supported by the improvement seen after plasma exchange (PLEX). Plasma Exchange which reduces IgG levels including pathogenic IgG autoantibody is used both in patients non-responsive to

inhibitors or immunosuppressive treatments and in patients experiencing myasthenic crisis (Gilhus and Verschuuren, 2015).

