6.4 Withdrawal criteria

Subjects are free to withdraw from the study at any time, without prejudice to their continued care.

Subjects MUST be withdrawn from the study if any of the following events occur:

- 1. Subject withdraws his/her consent.
- 2. Subject becomes pregnant during the study, as confirmed by a positive pregnancy test.

Subjects MUST discontinue IMP if any of the following events occur:

- Atiations thereof 1. Subject develops an illness or has a change in health status that would interfere with his/her continued participation, including but not limited to:
 - Subject has a serious infective episode requiring hospitalization or iv antibiotic therapy (including but not limited to bacteremia or sepsis, bacterial meningitis, osteomyelitis or septic arthritis, bacterial pneumonia, or visceral abscess).
 - Subject experiences a severe adverse event (AE) of GI disturbance or severe headache which is considered related to the IMP in the opinion of the investigator (Section 12.1.10).
 - Subject has an AE of infusion reaction of severe intensity requiring corticosteroid and/or epinephrine therapy.
 - Subject has an AE of anaphylactic reaction requiring corticosteroid and/or epinephrine therapy.
 - Subject has a TB test that is confirmed positive or any further evidence suggestive of potential TB infection (eg, exposure) and further examinations result in a diagnosis of active TB or LTBI (refer to Section 12.3.1) for further details and instructions.
 - If an NTMBI is identified during a study, the same withdrawal procedures as those _ used for an active TB infection identified during the study should be followed.
- 2. The sponsor or a regulatory agency requests withdrawal of the subject.
- 3. Subject is treated with rescue therapy (refer to Section 7.8.3).
- 4. Subject received rituximab during the Treatment Period.
- 5. Subject received prohibited concomitant medications (as defined in Section 7.8.2 of this protocol) during the Treatment Period.
- 6. According to the investigator's judgment this is in the best interest of the patient.
- 7. Meets criteria for liver injury (Section 6.4.1).
- 8. Subject has active suicidal ideation as indicated by a positive response (Yes) to either Question 4 or Question 5 of the "Since Last Visit" version of the C-SSRS. The subject should be referred immediately to a Mental Healthcare Professional.

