7.8.2 Prohibited concomitant treatments (medications and therapies)

The following concomitant medications and therapies are prohibited during the study:

- IVIg ٠
- All biologics including rituximab ٠
- Cyclophosphamide •
- Pimecrolimus •
- IPP-201101 (LupuzorTM) •
- PLEX •
- Immunoadsorption .
- Janvertensions or variations thereof. Janvertensions or variations thereof. Medications which could interfere with the function of the NMJ (and which therefore could impair subjects with MG), such as, but not limited to, the following medications. For a more REDACTED Authoritation detailed list please refer to the MGFA medication list (http://www.myasthenia.org/LivingwithMG/DrugstoAvoid.aspx).
 - botulinum toxin
 - aminoglycoside antibiotics
 - tetracycline antibiotics
 - penicillamine

If a subject needs or takes any prohibited medication or therapy (except IVIg, PLEX, or rituximab), the investigator will (where possible) discuss with the sponsor study physician and a decision will be made whether the subject can continue in the study or must be withdrawn. If the subject is treated with IVIg, rituximab, or PLEX, the subject must be withdrawn from the IMP, but should be encouraged to continue with Observation Period Visits.

For subjects who require a medical or surgical procedure that requires the use of general anesthesia, discussion must occur prior to the procedure with the medical monitor or study physician. In an emergency situation, discussion should occur as soon as possible after the procedure, such that a decision on the subject's continued participation in the study can be made.

Rescue medication 7.8.3

In the case of prolonged hypogammaglobulinemia the subject will be considered for treatment with prophylactic antimicrobial therapy. Subjects will be followed up until Ig levels return to within the normal range.

Aff, during the Treatment and Observation Period, in the opinion of the investigator, a subject has a significant deterioration in clinical condition, then rescue therapy such as IVIg or PLEX should be considered.

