9.2 Pharmacodynamics

The analysis of the PD data will be performed on the FAS with the exception of the total serum IgG and IgG subclasses results, which will be analyzed on the PD-PPS. All listings will be presented for the SS.

Any values that are BLQ or ALQ will be handled as described in [Section 4.2.2](#).

All analyses described in this section will be performed on the PD-PPS.

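### After rescue IVIg or PLEX the IgG and autoantibody values are confounded, and the SAP's pharmacodynamic rules can only keep them or drop the whole subject

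*SAP*

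**What the plan says.** - **Rescue.** If a subject deteriorates significantly in the Treatment or Observation Period, Protocol 7.8.3 says "then rescue therapy such as IVIg or PLEX should be considered". Protocol 7.8.2 also lists IVIg and PLEX under "The following concomitant medications and therapies are prohibited during the study". Under 6.4 a rescued subject stops IMP; under 7.8.2 that subject is encouraged to keep attending the Observation Period visits.
- **Sampling.** Table 5.1 draws total IgG and subclasses at every Observation Period visit, and MG-specific autoantibodies at Visits 15 and 20.
- **Effect of PLEX.** Protocol Section 2 describes "Plasma Exchange which reduces IgG levels including pathogenic IgG autoantibody".
- **Analysis set.** SAP 3.5.7 admits to the PD-PPS subjects in the FAS "consisting of those subjects who had no important protocol deviation affecting the serum concentrations of total serum IgG or IgG subclasses". For the Per-Protocol Set used for efficacy, SAP 3.5.5 adds: "Post-Baseline deviations will not necessarily lead to total exclusion of a subject from the PPS but may lead to exclusion of specific data". SAP 3.5.7 has no such sentence.
- **Autoantibodies.** SAP 9.2 begins "The analysis of the PD data will be performed on the FAS with the exception of the total serum" IgG and IgG-subclass results, and closes by assigning every analysis in that section to the PD-PPS.
- **Variables.** SAP 2.2.2.3 and 9.2.1 report the lowest total IgG and the largest fall from Baseline over the whole study.
- **Data handling.** SAP 4.2.3 covers values below or above quantification limits and missing values. It does not mention rescue.

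**The concern.** PLEX removes IgG, and IVIg is itself IgG. A sample taken after either no longer shows the effect of UCB7665 alone. It shows the rescue together with whatever drug effect remains.

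Rescue is plausible in this trial. Inclusion criterion 4 requires subjects whom the investigator would currently consider for treatment such as IVIg or PLEX, and one arm receives placebo through Dosing Period 1.

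The effect on total IgG is a secondary objective. The summaries are descriptive and the groups small, so one or two subjects can visibly move a mean. PLEX acts in the same direction as the drug, and Protocol 5.4.2 chose the regimen to imitate plasmapheresis, so a low value after PLEX cannot be told apart from a drug response by its size. Dropping rescued subjects altogether is no cure: it discards good data and leaves a set that favours subjects who did not need rescue.

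**Working it through.** The plan gives no figure on this point, and the redacted sample-size inputs do not bear on it. The check is therefore a comparison of the rules, followed by an illustration.

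**1. What the rules do with a rescued subject**

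| Classification of rescue | Total IgG and subclasses (PD-PPS) | Autoantibodies |
|---|---|---|
| Not an important deviation | All post-rescue values stay in | Stay in, on FAS or PD-PPS |
| Important deviation | Whole subject removed, pre-rescue values included | Stay in on the FAS; subject removed on the PD-PPS |

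Protocol 7.8.2 and 7.8.3 point in opposite directions on the classification. SAP 3.4 leaves the criteria to a separate document that was not available. As an example of the loss, a subject rescued between Visits 16 and 17 already has total IgG at Visits 2, 4, 6, 8, 9, 11, 13, 15 and 16. All nine would be discarded.

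**2. Which outputs are exposed**

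- The minimum and maximum decrease in IgG. With a whole-study window, a nadir after PLEX can be reported as the subject's maximum decrease.
- Visits 8 and 9 in the Period 1 arms after a late Period 1 rescue, where those samples are drawn. SAP 3.2.2 treats data up to the missed dose as planned.
- The four sequence groups, after rescue in Dosing Period 2 or the Observation Period.
- The by-visit correlations of patient-reported outcomes with IgG (SAP 8.3.8).

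**3. Size of the shift in a mean**

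Group sizes: 40 evaluable subjects allocated 1:1 give 40/2 = 20 per Period 1 arm, and 1:1 rerandomization gives about 20/2 = 10 per sequence group.

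Formula: shift = k × s / n, where k is the number rescued, n the group size and s the rescue-induced difference in percentage points of Baseline IgG. Neither k nor s is in the documents. I assume s = 30, 50 or 70; the upper end follows the 70% plasmapheresis-like target in Protocol 5.4.2.

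| k of n | s = 30 | s = 50 | s = 70 |
|---|---|---|---|
| 1 of 20 | 1.5 | 2.5 | 3.5 |
| 1 of 10 | 3 | 5 | 7 |
| 2 of 10 | 6 | 10 | 14 |

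The shift is downward after PLEX and, by assumption, upward in total IgG after IVIg. Dropping one subject instead leaves 19 of 20 or 9 of 10.

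**4. Upper bound for a recent IVIg infusion**

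Assumptions, none from the documents: total dose 1 to 2 g/kg, IgG distribution volume 0.07 to 0.10 L/kg, Baseline IgG 10 g/L, no elimination before sampling.

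- Rise = dose / volume: 1/0.10 = 10.0 g/L at the low end; 2/0.07 = 28.6 g/L at the high end.
- As a percentage of Baseline: 100% to 286%.
- Shift from one subject: 10.0 to 28.6 points for n = 10; 5.0 to 14.3 points for n = 20.

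This is an immediate peak. Observation visits are one to two weeks apart, so a typical sample would show less.

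**The case against.** **The deviation document and data evaluation meetings may already settle this.** They could. But SAP 3.4 uses important deviations to confirm exclusion from analysis sets, and nothing supplied gives a rule for individual pharmacodynamic values.

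**The consequence is limited.** This stands. No pharmacodynamic test is planned, medians and extremes appear beside the means, and listings on the Safety Set show every value together with medications and procedures. A careful reader could spot an odd subject, but the reported maximum decrease would still be wrong.

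**Some separation already exists.** This also stands. A subject rescued in Period 1 stops IMP, is not dosed in Period 2, and appears in a separate Observation Period group (SAP 3.1 and 3.6). A reader might infer that any rescue distorts the recovery curves of the four sequence groups; only rescue in Period 2 or later can.

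**Removing post-rescue values has its own selection effect.** Correct: later means would then describe only subjects who were not rescued. That is why an all-values summary has to accompany the main one.

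**Conclusion.** The concern holds as a cheap improvement to the descriptive pharmacodynamic analysis. The stated rules either keep confounded values or discard valid ones, and the whole-study window for the maximum decrease has no stop at rescue. For assumed individual effects of 30 to 70 points, one rescued subject moves a mean by 3 to 7 points in a group of 10 or 1.5 to 3.5 in an arm of 20. Soon after IVIg the shift could reach about 10 to 29 points in a group of 10, as an assumed peak. It is nil if nobody is rescued.

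Four stronger readings are tempting, and the documents do not support them:

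- *Post-rescue samples measure only the rescue.* Early ones also carry residual drug effect, so they are confounded, not empty of information.
- *Nothing is ever removed for autoantibodies.* SAP 9.2 names both the FAS and the PD-PPS, so the set is unresolved.
- *PLEX in a placebo subject creates an apparent drug benefit.* In the Period 1 comparison it lowers the placebo mean and shrinks the contrast.
- *The efficacy conclusion is at risk.* The primary QMG test does not use these data.

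**What to change.** Amend SAP 3.5.7 and 9.2 before unblinding:

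- State that rescue leads to exclusion of specific pharmacodynamic values, not of the subject.
- Exclude IgG, IgG-subclass and MG-specific autoantibody values dated after the first IVIg, SCIg, PLEX or immunoadsorption from the main summaries and plots.
- End the window for the minimum value and maximum decrease at that date.
- Set a convention for samples taken on the day of rescue, because SAP 4.2.7 notes that medication times are not recorded.
- List all values with a flag, and add a supportive summary that includes them.
- Reconcile the two statements in SAP 9.2 on the analysis set for autoantibodies.

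The cost is a few sentences, a flag from dates already collected, and one extra summary. Because SAP 3.8 leaves procedures uncoded, PLEX and immunoadsorption must be identified by review. The downside is fewer late values and later main means that exclude rescued subjects; the all-values summary shows how much that matters. No rescue rule or other clinical management changes.
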